**Table 1. Derivation for SARS-CoV-2 Infection**

| Baseline SARS-CoV-2 Status | Post-baseline assessments  |   | Endpoint: SARS-CoV-2 infection |
|-----------------------------------|---|---|---------------------------------------|
|                                   | PCR test post baseline  | bAb levels against SARS-CoV-2 Nucleocapsid                                    |                                       |
| Negative at Baseline of each part | Positive (either at nasal swab test, or at symptom-prompt nasal swab test) |   | Case                                  |
| Negative at Baseline of each part |   | Positive (at post-baseline visits) as measured by Roche Elecsys | Case                                  |

The date of documented infection will be the earlier of:

- Date of positive post-baseline RT-PCR result, or
- Date of positive serology test result based on bAb specific to SARS-CoV-2 nucleocapsid

In long-term analysis (including Part 2 Open-Label Phase), SARS-CoV-2 infection cases will be counted starting 14 days after the second injection of mRNA-1273, i.e. date of documented infection - date of the 2nd injection  $\geq$  14. SARS-CoV-2 infection cases will also be summarized based on tests performed at least 14 days after first dose of IP.

In booster dose analysis, SARS-CoV-2 infection cases will be counted starting 14 days after the booster dose of mRNA-1273, i.e. date of documented infection - date of the booster injection  $\geq$  14.

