#### **4.4. Blinding and Unblinding**

This study is conducted in three parts, Part 1 of this study will be open label, blinding procedures will not be applicable.

Part 2 of this study will be conducted in an observer-blind manner. The investigator, study staff, study participants, study site monitors, and Sponsor personnel (or its designees) will be blinded to the IP administered until study end, with certain exceptions, please refer to Section 8.1 of the protocol for details.

Part 3 is open label; however, if blinded administration is ongoing at the site, blinded procedure for Part 2 still applies.

The final analysis of all endpoints will be performed after all participants have completed all planned study procedures.

At the time of interim analysis, only pre-identified Sponsor and unblinded Contract Research Organization (CRO) team members as specified in the study Data Blinding Plan will be unblinded to review treatment level results and individual listings. Please also refer to [Section 6.9](#). Study sites will remain blinded to individual treatment assignments until the end of the study.

If a COVID-19 vaccine is authorized or licensed for a specific age group before the end of the study, please refer to protocol section 3.3 for unblinding and/or cross-over plans.

Participants under 6 years of age in Part 2 who have reached at least 6 months follow up after Dose 2 will be eligible for unblinding via a telephone call to learn which treatment they received. Participants who received placebo will be offered the option of cross-over vaccination with mRNA-1273 at that point as described above.

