### 5.2. Full Analysis Set

The Full Analysis Set (FAS) for Part 1 consists of all enrolled participants who receive at least 1 injection of IP, and the FAS for Part 2 consists of all randomly assigned participants who receive at least 1 injection of IP. Participants will be analyzed according to the treatment group for the treatment they actually received in Part 1 and will be analyzed according to the treatment group to which they were randomized in Part 2.

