### **Analysis periods**

The following analysis periods and treatment groups will be used for long-term and booster dose analysis.

- Long-term Analysis (Part 1 Open-Label Phase plus Part 2 Blinded and Open-Label Phase, until Booster Dose)

| Group               | Category                    | Start Date                      | End Date  |
|---------------------|-----------------------------|---------------------------------|---|
| mRNA-1273           | Safety                      | Date of First Dose of mRNA-1273 | Earliest date of booster dose (exclusive), study discontinuation, study completion, death, or data cutoff |
| Placebo - mRNA-1273 |                             |                                 | Earliest date of booster dose (inclusive), study discontinuation, study completion, death, or data cutoff |
| mRNA-1273           | Efficacy/
Immunogenicity | Date of First Dose of mRNA-1273 | Earliest date of booster dose (inclusive), study discontinuation, study completion, death, or data cutoff |
| Placebo - mRNA-1273 |                             |                                 | Earliest date of booster dose (inclusive), study discontinuation, study completion, death, or data cutoff |

- Long-term analysis (Part 1 Open-Label Phase plus Part 2 Blinded and Open-Label Phase, Regardless of Booster Dose) incidence rate will also be performed for the entire study period after the first dose of mRNA-1273 regardlesss of booster dose.

| Group               | Category                    | Start Date                      | End Date  |
|---------------------|-----------------------------|---------------------------------|---|
| mRNA-1273           | Safety                      | Date of First Dose of mRNA-1273 | Earliest date of study discontinuation, study completion, death, or data cutoff |
| Placebo - mRNA-1273 |                             |                                 | Earliest date of study discontinuation, study completion, death, or data cutoff |
| mRNA-1273           | Efficacy/
Immunogenicity | Date of First Dose of mRNA-1273 | Earliest date of study discontinuation, study completion, death, or data cutoff |
| Placebo - mRNA-1273 |                             |                                 | Earliest date of study discontinuation, study completion, death, or data cutoff |

- Part 3, First Two Doses of Primary Series Analysis

| Group           | Category | Start Date                      | End Date  |

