## 6.2. Background Characteristics

### 6.2.1. Subject Disposition

The number and percentage of subjects in the following categories will be summarized by age and vaccination group as defined in [Section 6.1](#) based on specific analysis datasets for Part 2 Open-label Phase, and Booster Dose Analysis separately:

For mRNA-1273 Primary Series Long-term and mRNA-1273 Booster:

- Full Analysis Set (Long-term Analysis)
- Full Analysis Set (Booster Dose Analysis)
- Immunogenicity Subset (Long-term Analysis)
- Immunogenicity Subset (Booster Dose Analysis)
- PP Immunogenicity Subset (Long-term Analysis)
- PP Immunogenicity Subset (Booster Dose Analysis)
- PP Immunogenicity Subset - Pre-booster SARS-CoV-2 Negative (Booster Dose Analysis)
- mITT1 Set (Long-term Analysis)
- mITT1 Set (Booster Dose Analysis)
- Solicited Safety Set (Booster Dose Analysis)
- Safety Set (Long-term Analysis)

- Safety Set (Booster Dose Analysis)

For mRNA-1273.214 Booster:

- Full Analysis Set (Booster Dose Analysis)
- Safety Set (Booster Dose Analysis)

For Part 3 First Two Doses of Primary Series, and Third Dose Analysis separately:

- Full Analysis Set
- Full Analysis Set (Third Dose Analysis)
- Solicited Safety Set
- Solicited Safety Set (Third Dose Analysis)
- Safety Set
- Safety Set (Third Dose Analysis)
- Immunogenicity Subset
- Immunogenicity Subset (Third Dose Analysis)
- PP Immunogenicity Subset
- PP Immunogenicity Subset (Third Dose Analysis)

The percentage will be based on subjects in that age and vaccination group within the Full Analysis Set for long-term analysis and booster/third dose analysis separately, except the Solicited Safety Set and Safety Set for which the percentages will be based on the age and vaccination group in the Safety Set (as treated) for long-term analysis and booster/third dose separately.

The number and percentage of subjects in each of the following disposition categories will be summarized by age and vaccination group based on the Randomization Set in Part 2:

- Received each dose of IP in Part 2 blinded phase
- Continuing and unblinded in Part 2 open-label phase
- Received each cross-over dose of IP in Part 2 open-label phase
- Prematurely discontinued study vaccine during Part 2 open-label phase and the reason for discontinuation

- Received mRNA-1273 booster dose in booster dose analysis for Part 2
- Received mRNA-1273.214 booster dose in booster dose analysis for Part 2
- Completed study

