## **6.5. Efficacy Analysis**

Exploratory analyses of incidence rates in COVID-19, SARS-CoV-2 infection, and asymptomatic infection will be performed using mITT1 Set. The mITT1 Set for the long-term analysis will be used for the incidence rate analysis in the long term including both the blinded and open-label phases; the mITT1 Set for the booster dose analysis will be used for the incidence analysis in the booster dose phase, unless otherwise specified. Subjects will be included in the vaccination group as defined in Section 6.1. As protocol amendment 9 was implemented in October 2022, no surveillance was conducted thereafter, and, therefore, no incidence rates will be calculated after October 2022.

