#### **6.5.1.3. Derivation of CDC Case Definition of COVID-19**

This is a secondary efficacy endpoint: the incidence of CDC Case Definition of COVID-19 starting 14 days after the second dose of mRNA-1273 in Part 2 open-label phase, and cases counted starting 14 days after the booster dose of mRNA 1273 in booster dose analysis. COVID-19 is defined as symptomatic disease based on the criteria specified in table listed below. Cases are defined as participants meeting clinical criteria based on both symptoms for COVID-19 and positive RT-PCR test results.

While Part 2 is still blinded for any age group, surveillance for COVID-19 symptoms will be conducted via biweekly telephone calls or eDiary. Subjects reporting CDC Case Definition of COVID-19 symptoms, as defined in Section 7.3.2 of the protocol, will be arranged an illness visit to collect a nasal swab for SARS-CoV-2.

Once the trial is unblinded for all age groups and thus no placebo comparator group is available going forward, COVID-19 surveillance will be discontinued, and COVID-19 cases will be reported under standard AE reporting per SoA only.

For this efficacy endpoint, a CDC Case Definition of COVID-19 case will be identified as a positive post-baseline RT-PCR test result, together with eligible symptoms, i.e. a positive PCR result of the eligible symptoms summarized below.

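### One supplementary long-term infection summary starts its 14-day lag at the first dose of IP, which as written is placebo for the crossover group, so the two groups get unequal counting windows

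*SAP*

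**What the plan says.** The file holds two SAPs: one for the Part 1 open-label and Part 2 blinded phases (the blinded-phase SAP), and one for the Part 2 open-label phase, boosters and Part 3 (the open-label SAP). The point lies in the second.

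Open-label SAP, section 6.5.1.1, under Table 1, gives two counting rules for SARS-CoV-2 infection in the long-term analysis. The main rule names the vaccine: "SARS-CoV-2 infection cases will be counted starting 14 days after the second injection of mRNA-1273". The next rule changes the reference dose: "SARS-CoV-2 infection cases will also be summarized based on tests performed at least 14 days after first dose of IP".

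Other places show what IP covers and when the long-term period begins:

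- Blinded-phase SAP, section 5.2: "the FAS for Part 2 consists of all randomly assigned participants who receive at least 1 injection of IP". Placebo recipients are in that set.
- Blinded-phase SAP, section 4.4: study staff and participants "will be blinded to the IP administered until study end", so IP is vaccine or placebo.
- Open-label SAP, section 6.2.1, disposition categories: "Received each dose of IP in Part 2 blinded phase". A separate row for the open-label phase also uses IP, but qualifies the dose as a crossover dose.
- Open-label SAP, section 6.1, analysis periods: for both long-term groups, efficacy starts at "Date of First Dose of mRNA-1273".

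**The concern.** The long-term analysis shows two groups: children given mRNA-1273 from the outset, and children given placebo who later crossed over (Placebo - mRNA-1273). A 14-day lag after the first dose is meant to leave out infections caught before a first vaccine dose could act. It does so only if it is measured from the first vaccine dose.

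Measured from the first dose of IP, it works for the original vaccine group, whose first IP dose is mRNA-1273. For the crossover group it is measured from placebo and excludes nothing after crossover. One sentence then yields two case definitions for groups tabulated in the same display, and the crossover group's figure includes early infections that the other group's figure leaves out.

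**Working it through.** The SAP gives no figure to reproduce here. The check applies the date rule as written and then sizes the effect under stated assumptions.

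**1. Counting rule.** A test counts if it falls on or after the first mRNA-1273 dose (section 6.1) and at least 14 days after the anchor dose (section 6.5.1.1). Let *g* be the days from the anchor dose to the first mRNA-1273 dose. The earliest countable test, in days after the first mRNA-1273 dose, is max(0, 14 − *g*).

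**2. Gap for crossover children.** Blinded-phase SAP section 4.4 makes children under 6 eligible for unblinding at least 6 months after Dose 2. With Dose 2 at 28 days and 6 months taken as 180 days, *g* is about 28 + 180 = 208. An early crossover with *g* = 28 is added as a check.

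| Group | Anchor: first IP | Anchor: first mRNA-1273 |
|---|---|---|
| mRNA-1273 (*g* = 0) | day 14 | day 14 |
| Placebo - mRNA-1273, *g* = 208 | max(0, 14 − 208) = day 0 | day 14 |
| Placebo - mRNA-1273, *g* = 28 | max(0, 14 − 28) = day 0 | day 14 |

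Any crossover 14 or more days after the first placebo dose gives day 0.

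**3. Does another rule restore the lag?**

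- Section 6.5.1.1 takes baseline before the first mRNA-1273 dose, and the crossover mITT1 Set (section 5.5) drops children with positive or missing tests before that dose. Both keep earlier detected infections out; neither adds 14 days afterwards.
- Person-time (section 6.5.2) runs from the first dose of each part, with no 14-day offset. If that means the first mRNA-1273 dose, as in section 6.1, both denominators start alike while the numerators do not, so the rate shifts as well as the count.

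**4. Illustrative size.** Assume a constant hazard, equal detection throughout, and follow-up of *T* days from the first vaccine dose. The relative excess of counted cases in the crossover group, against a proper lag, is 14/(*T* − 14):

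- *T* = 90: 14/76 = 18.4%
- *T* = 182: 14/168 = 8.3%
- *T* = 365: 14/351 = 4.0%

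**5. In absolute terms.** For 1,000 crossover children (the planned maximum on placebo in one age group), the extra window is 1,000 × 14/365.25 = 38.3 person-years. The SAP gives no attack rates. At assumed rates of 0.05, 0.1, 0.5 and 1.0 per person-year, this is about 1.9, 3.8, 19.2 and 38.3 extra counted infections.

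**The case against.** **The authors may have meant the first IP dose of the long-term part.** Section 6.2.1 of the open-label SAP does call crossover injections IP, and section 1 treats injection of IP, injection and dose as interchangeable. The neighbouring rules (baseline, period start) take the first mRNA-1273 dose as origin. A lag with no effect in one group looks like wording carried over from section 3.2 of the blinded-phase SAP, where it suits both arms. This reading is possible. But section 6.2.1 needs a qualifier to reach it, section 6.5.1.1 has none, and the preceding sentence names mRNA-1273. A programmer following the text would take the placebo date.

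**The reach is narrow.** This stands. The sentence governs one additional summary of one endpoint, and sections 2.1 and 6.5 make these incidence analyses descriptive or exploratory. A reader might infer that a comparison is biased against crossover vaccination. The documents do not support that: section 6.5.2 plans rates by group with exact Poisson intervals and no between-group test or ratio. The groups also started vaccine at different calendar times, so their rates are not directly comparable under either anchor.

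**The percentages are hypothetical.** This also stands. The crossover schedule (Appendix E) lists no nasal swab or blood draw, so detection in the first 14 days is probably below that at later routine sampling visits. That makes 4% to 18% more likely too high than too low. Assuming the hazard halves after day 14 would double the figures, but nothing in the documents gives that ratio.

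**A stronger reading of the post-Dose-2 wording.** Section 6.5.1.3 defines "the incidence of CDC Case Definition of COVID-19 starting 14 days after the second dose of mRNA-1273 in Part 2 open-label phase", with similar phrasing in 6.5.1.2 and 6.5.1.4, although section 6.5 describes "incidence rate analysis in the long term including both the blinded and open-label phases". A reader might infer that three of the four endpoints have no counting start for the original vaccine group, whose second dose was not given in the open-label phase. The documents largely answer this. The opening of 6.5.1.1 uses the same phrase, and the text under Table 1 shows that the second mRNA-1273 injection is meant. Section 3.1 also refers back to the blinded-phase endpoints, which count from 14 days after the second dose, and for that group the second dose is mRNA-1273. What remains is a wording inconsistency.

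**Conclusion.** The point holds for one sentence. Read as written, the supplementary long-term infection summary counts from day 0 after the first vaccine dose in the Placebo - mRNA-1273 group and from day 14 in the mRNA-1273 group. This rests on IP including placebo, which sections 4.4 and 5.2 of the blinded-phase SAP support, and on no other rule resetting the anchor; none was found.

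The importance is minor. The main post-Dose-2 count and all hypothesis tests are untouched. The documents give neither attack rates nor crossover dates, so the size cannot be fixed; the 4% to 18% range for 12 to 3 months of follow-up is an illustration and probably an upper range.

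**What to change.** In the open-label SAP, section 6.5.1.1, text under Table 1, replace *first dose of IP* by *first dose of mRNA-1273*. The earliest countable test is then day 14 after the first vaccine dose in both groups.

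As a wording alignment only, state the post-Dose-2 start in the opening of 6.5.1.1 and in 6.5.1.2, 6.5.1.3 and 6.5.1.4 as it stands under Table 1, namely the second injection of mRNA-1273, without tying it to the open-label phase.

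The cost is a text edit and one reference date in the case derivation. No new data are needed, and no clinical procedure changes. If the summary has already been produced, it needs one rerun for the crossover group, unless the programs already used the first mRNA-1273 date.

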#### **6.5.1.2. Derivation of Asymptomatic SARS-CoV-2 Infection**

This is a secondary efficacy endpoint: the incidence of asymptomatic SARS-CoV-2 infection measured by RT-PCR and/or serology tests obtained at post-baseline visits counted starting 14 days after the second injection of mRNA-1273 in Part 2 open-label

Phase, and cases counted starting 14 days after the booster dose of mRNA 1273 in booster dose analysis, in participants with negative SARS-CoV-2 status at baseline of each part.

Asymptomatic SARS-CoV-2 infection is identified by absence of symptoms and infections as detected by RT-PCR or serology tests. Specifically:

- Absent of COVID-19 symptoms
- AND at least one from below:
  - bAb level against SARS-CoV-2 nucleocapsid protein negative (as measured by Roche Elecsys) at baseline of each part that becomes positive (as measured by Roche Elecsys) post-baseline, OR
  - Positive RT-PCR test post-baseline (at scheduled or unscheduled/illness visits)

The date of documented asymptomatic infection is the earlier date of positive serology test result based on bAb specific to SARS-CoV-2 nucleocapsid due to infection, or positive RT-PCR at scheduled visits, with absence of symptoms.

#### **6.5.1.3. Derivation of CDC Case Definition of COVID-19**

This is a secondary efficacy endpoint: the incidence of CDC Case Definition of COVID-19 starting 14 days after the second dose of mRNA-1273 in Part 2 open-label phase, and cases counted starting 14 days after the booster dose of mRNA 1273 in booster dose analysis. COVID-19 is defined as symptomatic disease based on the criteria specified in table listed below. Cases are defined as participants meeting clinical criteria based on both symptoms for COVID-19 and positive RT-PCR test results.

While Part 2 is still blinded for any age group, surveillance for COVID-19 symptoms will be conducted via biweekly telephone calls or eDiary. Subjects reporting CDC Case Definition of COVID-19 symptoms, as defined in Section 7.3.2 of the protocol, will be arranged an illness visit to collect a nasal swab for SARS-CoV-2.

Once the trial is unblinded for all age groups and thus no placebo comparator group is available going forward, COVID-19 surveillance will be discontinued, and COVID-19 cases will be reported under standard AE reporting per SoA only.

For this efficacy endpoint, a CDC Case Definition of COVID-19 case will be identified as a positive post-baseline RT-PCR test result, together with eligible symptoms, i.e. a positive PCR result of the eligible symptoms summarized below.

### Derivation for CDC Case Definition of COVID-19

|                           | COVID-19   |
|---------------------------|---|
| Post-baseline PCR results | Positive, AND  |
| Systemic Symptoms         | at least ONE of the following systemic symptoms: Fever (temperature $\geq 38^{\circ}\text{C}/\geq 100.4^{\circ}\text{F}$ ) or chills (of any duration, including $\leq 48$ hours), fatigue, headache, myalgia, nasal congestion or rhinorrhea, new loss of taste or smell, sore throat, abdominal pain, diarrhea, nausea/vomiting, poor appetite/poor feeding; OR |
| Respiratory symptoms      | at least ONE of the following respiratory signs/symptoms: cough (of any duration, including $\leq 48$ hours), shortness of breath or difficulty breathing (of any duration, including $\leq 48$ hours).   |

#### 6.5.1.4.Derivation of COVID-19 (P301 Primary Definition)

This is a secondary efficacy endpoint: the incidence of P301 primary definition of COVID-19 starting 14 days after the second dose of mRNA-1273 in Part 2 open-label phase, and cases counted starting 14 days after the booster dose of mRNA 1273 in booster dose analysis.

The P301 primary definition of COVID-19 is defined by the following criteria:

- At least TWO of the following systemic symptoms: Fever ( $\geq 38^{\circ}\text{C}/\geq 100.4^{\circ}\text{F}$ ), chills, myalgia, headache, sore throat, new olfactory and taste disorder(s), OR
- The participant must have experienced at least ONE of the following respiratory signs/symptoms: cough, shortness of breath or difficulty breathing, OR clinical or radiographical evidence of pneumonia; AND
- At least one positive RT-PCR test for SARS CoV-2

The date of documented COVID-19 (P301 Primary Definition) will be the later date of :

- Date of the positive RT-PCR test (prompt by symptom)
- Date of eligible symptom(s), defined as earliest of
  - Respiratory symptom: earliest date of an eligible respiratory symptom is reported
  - Systemic symptoms: earliest date of the eligible systemic symptoms are reported

and the two dates should be within 14 days of each other.

### **6.5.2. Analysis Method**

The number and percentage of subjects who had an event will be summarized in the mITT1 Set for the long-term analysis and booster dose phase analysis

The incidence rate will be provided by age and vaccination group if applicable, calculated as the number of cases divided by the total person-time. The 95% CI of the incidence rate will be calculated using the exact method (Poisson distribution) and adjusted by person-time.

Person-time is defined as the total time from date of the 1st dose of each part to the date of event, dose date in next part, last date of study participation, censoring time, or efficacy data cutoff date, whichever is earlier.

Incidence rate will also be analyzed by time period or by calendar month.

